17.8. Monitoring

The sponsor will perform on-site monitoring visits as frequently as necessary. The monitor will record dates of the visits in a study site visit log that will be kept at the study site. At these visits, the monitor will compare a sample of the data entered into the CRFs with the hospital or clinic records (source documents). The nature and location of all source documents will be identified to ensure that all sources of original data required to complete the CRF are known to the sponsor and study-site personnel and are accessible for verification by the sponsor study-site contact. If electronic records are maintained at the study site, the method of verification must be discussed with the study-site personnel.

Remote data surveillance will be performed to monitor the study. Key subject demographic data, site performance data and other key variable data will be monitored remotely as part of routine data surveillance on a monthly basis for all sites and be compared to the results seen overall for that country and region. Sites identified as having subjects with data that deviates substantially from the norm may also be subject to additional in-person monitoring visits.

Direct access to source documentation (medical records) must be allowed for the purpose of verifying that the data recorded in the CRF are consistent with the original source data. Findings from this review of eCRFs and source documents will be discussed with the study-site personnel. The sponsor expects that, during monitoring visits, the relevant study-site personnel will be available, the source documentation will be accessible, and a suitable environment will be provided for review of study-related documents. The monitor will meet with the investigator on a regular basis during the study to provide feedback on the study conduct.

In addition to on-site monitoring visits, remote contacts can occur. It is expected that during these remote contacts, study-site personnel will be available to provide an update on the progress of the study at the site.

17.9. Study Completion/Termination

17.9.1. Study Completion

The study is considered completed with the last study assessment for the last subject participating in the study. The final data from the study site will be sent to the sponsor (or designee) after completion of the final subject assessment at that study site, in the time frame specified in the Clinical Trial Agreement.

17.9.2. Study Termination

The sponsor reserves the right to close the study site or terminate the study at any time for any reason at the sole discretion of the sponsor. Study sites will be closed upon study completion. A study site is considered closed when all required documents and study supplies have been collected and a study-site closure visit has been performed.

The investigator may initiate study-site closure at any time, provided there is reasonable cause and sufficient notice is given in advance of the intended termination.

Reasons for the early closure of a study site by the sponsor or investigator may include but are not limited to:

- Failure of the investigator to comply with the protocol, the requirements of the IEC/IRB or local health authorities, the sponsor's procedures, or GCP guidelines
- Inadequate recruitment of subjects by the investigator
- Discontinuation of further study drug development

17.10. On-Site Audits

Representatives of the sponsor's clinical quality assurance department may visit the study site at any time during or after completion of the study to conduct an audit of the study in compliance with regulatory guidelines and company policy. These audits will require access to all study records, including source documents, for inspection and comparison with the CRFs. Subject privacy must, however, be respected. The investigator and study-site personnel are responsible for being present and available for consultation during routinely scheduled study-site audit visits conducted by the sponsor or its designees.

Similar auditing procedures may also be conducted by agents of any regulatory body, either as part of a national GCP compliance program or to review the results of this study in support of a regulatory submission. The investigator should immediately notify the sponsor if he or she has been contacted by a regulatory agency concerning an upcoming inspection.

17.11. Use of Information and Publication

All information, including but not limited to information regarding rivaroxaban or the sponsor's operations (eg, patent application, formulas, manufacturing processes, basic scientific data, prior clinical data, formulation information) supplied by the sponsor to the investigator and not previously published, and any data, including exploratory research data, generated as a result of this study, are considered confidential and remain the sole property of the sponsor. The investigator agrees to maintain this information in confidence and use this information only to accomplish this study, and will not use it for other purposes without the sponsor's prior written consent.

The investigator understands that the information developed in the study will be used by the sponsor in connection with the continued development of rivaroxaban, and thus may be disclosed as required to other clinical investigators or regulatory agencies. To permit the information

derived from the clinical studies to be used, the investigator is obligated to provide the sponsor with all data obtained in the study.

The results of the study will be reported in a Clinical Study Report generated by the sponsor and will contain CRF data from all study sites that participated in the study, and direct transmission of clinical laboratory data from a central laboratory into the sponsor's database. Recruitment performance or specific expertise related to the nature and the key assessment parameters of the study will be used to determine a coordinating investigator. Results of exploratory analyses performed after the Clinical Study Report has been issued will be reported in a separate report and will not require a revision of the Clinical Study Report. Study subject identifiers will not be used in publication of results. Any work created in connection with performance of the study and contained in the data that can benefit from copyright protection (except any publication by the investigator as provided for below) shall be the property of the sponsor as author and owner of copyright in such work.

Consistent with Good Publication Practices and International Committee of Medical Journal Editors guidelines, the sponsor shall have the right to publish such primary (multicenter) data and information without approval from the investigator. The investigator has the right to publish study site-specific data after the primary data are published. If an investigator wishes to publish information from the study, a copy of the manuscript must be provided to the sponsor for review at least 60 days before submission for publication or presentation. Expedited reviews will be arranged for abstracts, poster presentations, or other materials. If requested by the sponsor in writing, the investigator will withhold such publication for up to an additional 60 days to allow for filing of a patent application. In the event that issues arise regarding scientific integrity or regulatory compliance, the sponsor will review these issues with the investigator. The sponsor will not mandate modifications to scientific content and does not have the right to suppress information. For multicenter study designs and substudy approaches, secondary results generally should not be published before the primary outcomes of a study have been published. Similarly, investigators will recognize the integrity of a multicenter study by not submitting for publication data derived from the individual study site until the combined results from the completed study have been submitted for publication, within 12 months of the availability of the final data (tables, listings, graphs), or the sponsor confirms there will be no multicenter study publication. Authorship of publications resulting from this study will be based on the guidelines on authorship, such as those described in the Uniform Requirements for Manuscripts Submitted to Biomedical Journals, which state that the named authors must have made a significant contribution to the design of the study or analysis and interpretation of the data, provided critical review of the paper, and given final approval of the final version.

Registration of Clinical Studies and Disclosure of Results

The sponsor will register and/or disclose the existence of and the results of clinical studies as required by law.

REFERENCES

1. AHRQ Center for Delivery, Organization, and Markets, Healthcare Utilization Project Inpatient Sample, 1993-2008.

Attachment 1: Efficacy Outcomes

All efficacy evaluations and outcomes described in Section 9.2 will be evaluated and adjudicated by the CEC (defined below). Safety outcomes are defined in Section 9.5.

1. Death will be assigned to 1 of the following:
 - a. CV death
 - i) VTE-related
 - (1) VTE-related death – death due to confirmed PE documented by objective testing or autopsy,
 - (2) VTE-related, PE cannot be ruled out – death, which cannot be attributed to a documented cause and for which pulmonary embolism cannot be ruled out (unexplained death)
 - ii) Other CV death
 - b. Non-CV death – death not included in 1 of the above categories
2. Symptomatic DVT – displaying signs or symptoms of proximal or distal lower extremity DVT, upper extremity DVT, or other DVT and confirmed by adjudication, based on 1 or more of the following diagnostic criteria:
 - a. a non-compressible venous segment on compression ultrasonography, or in patients with a history of previous DVT, either a new non-compressible venous segment or a substantial increase (4 mm or more) in the diameter of the vein during full compression in a previously abnormal segment on ultrasonography, or
 - b. the presence of an intraluminal filling defect on venography, or
 - c. DVT documented at autopsy.

If in patients with history of previous DVT or incomplete documentation of the previous episode is available, additional criteria may be integrated into the adjudication of the current event, such as: ultrasonography appearance of the thrombus, or D-dimer at presentation. Soleal or muscular branch DVTs, lower extremity superficial DVT will not be included. The totality of available clinical, imaging and laboratory findings should be considered

3. Symptomatic PE – displaying signs or symptoms suggestive of PE and confirmed by adjudication based on 1 or more of the following diagnostic criteria:
 - a. an intraluminal filling defect on computed tomography (CT) angiography or spiral CT, or
 - b. an intraluminal filling defect on pulmonary angiography or cutoff of a vessel more than 2.5 mm in diameter, or
 - c. a perfusion lung scan defect of at least 75% of a segment with corresponding normal ventilation (high probability ventilation-perfusion (V-Q) scan), or
 - d. a non-high probability V-Q scan abnormality associated with DVT documented by ultrasonography or venography, or
 - e. in the absence of imaging test in a hemodynamically unstable patient, evidence of right ventricular dysfunction by transthoracic or trans esophageal echocardiogram (ESC criteria), or
 - f. PE documented at autopsy.

The anatomic extent of PE will be classified by the adjudication committee as either segmental or greater, or sub-segmental. The totality of available clinical, imaging and laboratory findings should be considered.

4. Myocardial infarction

Requires combination of evidence of myocardial necrosis (either changes in cardiac biomarkers or post-mortem pathological findings), and supporting information from clinical presentation, ECG changes or the results of myocardial imaging or coronary artery imaging. The totality of available clinical, ECG and cardiac biomarker should be considered:

1. Clinical Presentation consistent with the diagnosis of myocardial ischemia and infarction, taking into account differential conditions associated with elevations in cardiac biomarkers
2. Biomarker elevations
 - a. Elevations relative to URL in CK, CK-MB or troponin
3. ECG changes
 - a. ECG manifestations of acute myocardial ischemia (in absence of left ventricular hypertrophy and left bundle branch block); abnormalities may be lesser in patients with abnormal biomarkers
 - i. New ST elevation at the J point in 2 contiguous leads with the cut-points: ≥ 0.1 mV in all leads other than leads V2-V3 where the following cut-points apply: ≥ 0.2 mV in men ≥ 40 years (≥ 0.25 mV in men < 40 years) or ≥ 0.15 mV in women
 - ii. New horizontal or down-sloping ST depression ≥ 0.05 mV in 2 contiguous leads and/or new T inversion ≥ 0.1 mV in 2 contiguous leads with prominent R wave or R/S ratio > 1
 - b. Criteria for pathological Q-wave
 - i. Any Q-wave in leads V2-V3 (abnormalities may be lesser in patients with abnormal biomarkers) 0.02 seconds or QS complex in leads V2 and V3
 - ii. Q-wave ≥ 0.03 seconds and ≥ 0.1 mV deep or QS complex in leads I, II, aVL, aVF, or V4-V6 in any 2 leads of a contiguous lead grouping (I, aVL, V1-V6, II, III, and aVF; the same criteria are used for supplemental leads V7-V9 and for the Cabrera frontal plane lead grouping)
 - c. ECG changes with prior myocardial infarction
 - i. Pathological Q-waves, as defined above
 - ii. R-wave ≥ 0.04 seconds in V1-V2 and R/S ≥ 1 with a concordant positive T-wave in the absence of a conduction defect
 - d. Criteria for prior myocardial infarction
 - i. Pathological Q waves with or without symptoms in the absence of non-ischemic causes
 - ii. Imaging evidence of a region of loss viable myocardium that is thinned and fails to contract, in the absence of a non-ischemic change
 - iii. Pathological findings of a prior myocardial infarction

5. Stroke – an acute episode of focal or global neurological dysfunction caused by non-traumatic brain or spinal cord injury as a result of hemorrhage or infarction

Attachment 2: Suspected Event Supporting Documentation

The following supporting material, if available, will be requested to be submitted for each suspected event by the investigative site. The totality of available clinical, imaging and laboratory findings should be considered. Supporting materials to be completed/collected, not limited to:

1. Death with cause
 1. Complete Death eCRF data
 2. Hospital admission history and physical/death summary
 3. Autopsy reports

2. Suspected Symptomatic deep venous thrombosis (DVT)
 1. Complete Symptomatic Deep Vein Thrombosis eCRF data
 2. Imaging
 3. Hospital admission history and physical
 4. Hospital discharge summary
 5. Duplex ultrasound
 6. Venography
 7. Computed tomography (CT) scan or MRI
 8. D-Dimer
 9. Autopsy reports

3. Suspected Symptomatic PE
 1. Complete Symptomatic Pulmonary Embolism eCRF data
 2. Hospital admission history and physical
 3. Hospital discharge summary
 4. D-Dimer
 5. High resolution CT pulmonary angiogram or helical chest CT scan
 6. Ventilation/perfusion scan
 7. Transthoracic or transesophageal echocardiogram in hemodynamically unstable patient
 8. MRI
 9. Chest X-Ray
 10. Duplex Ultrasound or venography
 11. Electrocardiogram
 12. Autopsy reports

4. Suspected Myocardial infarction / acute coronary syndrome
 1. Complete Myocardial Infarction eCRF data
 2. Hospital admission history and physical
 3. Hospital discharge summary
 4. Electrocardiogram
 5. Cardiac Biomarkers
 6. Autopsy reports

5. Suspected Stroke / transient ischemic attack
 1. Complete Stroke eCRF data
 2. Hospital admission history and physical

3. Hospital discharge summary
 4. Computed tomography (CT) scan
 5. Magnetic resonance imaging (MRI)
6. Suspected Major bleeding (MB)
1. Complete Bleeding Event eCRF data
 2. Hospital admission history and physical
 3. Hospital discharge summary
 4. Procedure notes
 5. CBC laboratory test
7. Suspected Non-major clinically relevant bleeding (NMCR)
1. Complete Bleeding Event eCRF data
 2. Hospital admission history and physical
 3. Hospital discharge summary
 4. Procedure notes
 5. CBC laboratory test
8. Suspected Other Bleeding
1. Complete Bleeding Event eCRF data
 2. Hospital admission history and physical
 3. Hospital discharge summary
 4. Procedure notes
 5. CBC laboratory test

Attachment 3: Pharmacokinetic Sample Collection and Handling**Materials and Labeling**

Blood must be collected in glass or plastic blood collection tubes (eg, Vacutainer[®]) containing appropriate anticoagulants. Resulting plasma samples must be stored in polypropylene storage tubes. No tubes with separation gel should be used.

Use of alternative materials will not result in a protocol amendment if preapproved by the Bio-analysis Scientist.

All tubes and containers will be labeled with preprinted labels. The preprinted information will include the study number, CRF identification number (CRF I.D. #), treatment arm or treatment period, scheduled sampling day and time as stipulated in the flow chart, and the analyte name if applicable. No other information will be written on the labels. Labels should be attached to the storage tubes at least 12 hours before being frozen to ensure proper adherence.

Labels should be applied to the sample tubes as follows:

- Apply labels to the sample tubes so that they do not overlap and obscure any information. If possible, expose an area between the 2 ends of the label to allow viewing of the contents of the tube.
- Do not alter the orientation of the label on the sample tube.
- Apply labels to all tubes in the same manner.

Preparation of Plasma Pharmacokinetic Samples for Rivaroxaban

- Collect 2 mL of blood into the appropriate K₂EDTA -containing collection tube (eg, Vacutainer) at each time point.
- Record the exact date and time of sampling in the CRF.
- Gently invert the tubes 8 to 10 times to afford mixing, before processing.
- Centrifuge blood samples at room temperature within 1 hour of collection in a clinical centrifuge at 1,300 g for 15 minutes or centrifuge for 10 minutes at 1,500 - 1,600 g, unless otherwise specified by the supplier, to yield approximately 1 mL of plasma from each 2 mL whole blood sample.
- Transfer all separated plasma immediately with a clean, disposable glass or polyethylene pipette (use 1 new pipette per sample) to a pre-labeled storage tube (1.8 mL NUNC tubes).
- Store plasma samples in an upright position in a freezer, at a set temperature of -20°C until transfer to the bio-analytical facility.
- The time between blood collection and freezing the plasma will not exceed 2 hours.
- Ship specimens according to the instructions provided.
- Ship specimens to the bio-analytical facility, sorted by subject, by sample collection date and time.
- Questions regarding handling the plasma PK specimens should be addressed to the contact person for the sponsor.
- Alternative procedures will not result in a protocol amendment if approved by the Bioanalysis Scientist.

Please refer to the Study Lab Manual for proper shipping instructions.

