3.2. Study Design Rationale

Study Population

Medically ill patients, ie, patients who have been hospitalized for the treatment of acute medical illnesses, are at high risk for the development of VTE during their hospital stay and immediately after hospital discharge. These are important clinical events that profoundly impact medically ill patients, and constitute a large burden in terms of health care provision. High-risk medically ill subjects have been chosen for this study because post-hospital discharge thromboprophylaxis is a useful therapeutic approach to reduce the risk of increased VTE events, morbidity and mortality in these patients and would meet an unmet medical need. The pharmacology, mechanism of action, and previous clinical studies of rivaroxaban suggest that rivaroxaban will reduce the risk of VTE events and VTE-related death (death due to PE or death in which PE cannot be ruled out as the cause). The timing of enrollment, randomization and treatment phase for these subjects has been chosen because there is a high rate of VTEs and VTE-related mortality during this post-hospitalization phase, particularly during the first 2 months after discharge^{18,37}. Compared with previous studies, there are several differences in the choice of study populations to reduce the bleeding risk (Section 1.1).

Blinding Control Study Phase/Periods Treatment Groups

This randomized, double-blind, placebo-controlled, parallel-group, multicenter, event-driven design, is a scientifically rigorous approach for evaluating the efficacy and safety of rivaroxaban in high-risk, medically ill patients and meets the registration requirements for a superiority study.

Randomization and stratification will be used to minimize bias in the assignment of subjects to treatment groups, to increase the likelihood that known and unknown subject attributes

(eg, demographic and baseline characteristics) are evenly balanced across treatment groups, and to enhance the validity of statistical comparisons across treatment groups. Subjects will be randomized by strata (by subjects with CrCl \geq 30 mL/min and $<$ 50 mL/min versus subjects with CrCl \geq 50 mL/min, and by country). Double-blinded treatment will be implemented to reduce potential bias during data collection and evaluation of clinical outcomes.

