5. TREATMENT ALLOCATION AND BLINDING

Treatment Allocation

Procedures for Randomization and Stratification

Central randomization will be implemented in this study. Subjects will be randomly assigned to 1 of 2 treatment groups based on a computer-generated randomization schedule prepared before the study under the supervision of the sponsor. The randomization will be balanced by using randomly permuted blocks and will be stratified by subjects with CrCl ≥ 30 and < 50 mL/min versus subjects with CrCl ≥ 50 mL/min and by country. Enrollment may be capped for subgroups with certain baseline characteristics (eg, index hospitalization duration, reason for index hospitalization, risk score, and index hospitalization thromboprophylaxis) or by country or region. If a decision is made to institute capping, the site will receive a written communication with instructions for implementation and a request for confirmation of receipt.

The IWRS will assign a unique treatment code, which will dictate the treatment assignment and matching study drug kits for the subject. The requestor must use his or her own user identification and personal identification number when contacting the IWRS, and will then give the relevant subject details to uniquely identify the subject.

Blinding

The investigator will not be provided with randomization codes. The codes will be maintained within the IWRS, which has the functionality to allow the investigator to break the blind for an individual subject.

Data that may potentially unblind the treatment assignment (ie, events that contribute to the primary and secondary outcome or treatment allocation) will be handled with special care to ensure that the integrity of the blind is maintained and the potential for bias is minimized. This can include making special provisions, such as segregating the data in question from view by the investigators, clinical team, or others as appropriate until the time of database lock and unblinding.

Unblinding

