9.3. Pharmacokinetics

9.3.1. Evaluations

Pharmacokinetic samples will be collected at selected countries and sites that can provide the logistical requirements necessary for the PK sampling. Fasting is not required to validate the population PK model. Four sparse blood samples will be collected at 2 visits for about 600 subjects (300 subjects in rivaroxaban subjects [200 subjects in the 10 mg daily and 100 in the 7.5 mg daily group] and 300 in the placebo group) (Table 3 and Table 4). These data will be used to describe drug exposure. Blood samples (2.0 mL each) for determination of rivaroxaban plasma concentrations will be collected at the time points indicated in the TIME AND EVENTS SCHEDULE. The exact date and time of the administration of the current dose (plus the 2 preceding doses) and the precise actual time of blood sample collection must be accurately documented in the eCRF or laboratory requisition form, as appropriate. The PK sub-study will only be conducted at specific sites (ie, those that have the capability to draw, process, and store the PK samples), where all subjects screened will be given the choice to participate. For the PK sample population, drug should always be taken in the morning. At the Day 7 visit, the study drug must be administered under supervision following the collection of the trough sample. At the Day 21 visit, subjects will take the study medication at home in the morning and visit the clinic for PK sampling. At the Day 21 visit, the date and time of the dose administration must be recorded and there needs to be a minimum of 3 hours between sample collections. Subjects may be confined to the study site during PK sampling, if considered appropriate. Samples will be used to evaluate the PKs of rivaroxaban (Attachment 3).

Table 3 Pharmacokinetic Suggested Sampling Schedule

PK Blood sampling (selected sites and subjects)	Day 7		Day 21	
	Pre-dose	Hours Post-dose	Hours Post-dose	
		1-4 Hours	3-7 Hours	7-12 Hours
	X	X	X	X

Table 4: Summary of PK Suggested Observations for Rivaroxaban Arm

Active doses (mg/day)	Total number of subjects with measured samples on Rivaroxaban	Number of Measurements Plasma Concentrations
7.5	100	400
10	200	800
Total	300	1,200

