Attachment 4: Symptom Assessment

During all contacts, the treatment and clinical course of the subject is to be evaluated using a standard list of questions. Please ask the subject systematically the following questions -

1. Since the last contact did you experience new or increased?

Shortness of Breath	Yes  No 
Chest Pain especially while breathing	Yes  No 
Cough	Yes  No 
Blood in Sputum	Yes  No 
Dizziness or Fainting	Yes  No 
Rapid Breathing	Yes  No 
Rapid Heart Rate	Yes  No 
Blue Lips or Fingers	Yes  No 
Weakness on one side of face/body	Yes  No 
Fever	Yes  No 

If PE is clinically suspected, perform objective testing and complete the adjudication package as described in [Attachment 2 \(Suspected Event Supporting Documentation\)](#) of the protocol.

2. Since the last contact did you experience new or increased?

Calf pain, tenderness or swelling	Yes  No 
Appearance of veins on the surface of the skin on legs	Yes  No 
Tenderness along deep veins of legs	Yes  No 
Swelling of entire leg	Yes  No 
Puffiness of leg	Yes  No 

If DVT is clinically suspected, perform objective testing and complete the adjudication package as described in [Attachment 2 \(Suspected Event Supporting Documentation\)](#) of the protocol.

3. Since the last contact did you experience any?

Bleeding	Yes  No 
----------	--

If yes, complete the adjudication package as described in [Attachment 2 \(Suspected Event Supporting Documentation\)](#) of the protocol.

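### Protocol Attachment 3 allows PK tube labels handled at sites to carry the treatment arm, which is inconsistent with the blinding provisions of Section 5

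*Protocol*

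**What the plan says.** Attachment 3 of the protocol is current text, not part of the amendment history. It says of the PK samples: "All tubes and containers will be labeled with preprinted labels". On content: "The preprinted information will include the study number, CRF identification number (CRF I.D. #), treatment arm or treatment period". The list continues with the scheduled sampling day and time and, if applicable, the analyte name, and closes with "No other information will be written on the labels". Plasma is transferred "to a pre-labeled storage tube (1.8 mL NUNC tubes").

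Section 9.3.1 places this work at the study sites: "The PK sub-study will only be conducted at specific sites (ie, those that have the capability to draw, process, and store the PK samples"). The sub-study covers about 600 subjects: 300 on rivaroxaban and 300 on placebo.

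Section 5 says "The investigator will not be provided with randomization codes", and that the codes are held in the IWRS. It adds that data which might unblind, treatment allocation included, are to be handled with special care. The measures it mentions are optional, and PK labels are not among them. Section 3.2 gives the purpose of the blind: "Double-blinded treatment will be implemented to reduce potential bias during data collection and evaluation of clinical outcomes".

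**The concern.** In a parallel-group, placebo-controlled trial the arm is the allocation. A label that shows it next to a subject identifier, on a tube handled at the site, would unblind whoever reads it.

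This matters more here than in a trial with scheduled imaging. The primary outcome counts symptomatic events and VTE-related deaths, and the diagnostic work-up follows local suspicion. Attachment 4 instructs: "If PE is clinically suspected, perform objective testing and complete the adjudication package". For PK subjects the Day 7 and Day 21 visits must take place in the clinic, and the scripted symptom questions and the review for suspected outcomes fall at those same visits. Someone who knew the arm might test for PE or DVT more readily in placebo subjects, or report minor bleeding more readily in rivaroxaban subjects. Blinded adjudication covers the events that are submitted. It cannot recover one that was never investigated.

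**Working it through.** **Reproducing the plan's own figures**
- Rivaroxaban PK subjects (Section 9.3.1, Table 4): 200 on 10 mg + 100 on 7.5 mg = 300.
- All PK subjects: 300 + 300 placebo = 600. Section 3.1 says up to 600 and Section 9.3.1 says about 600, so this is a ceiling or an approximation.
- Measured rivaroxaban concentrations at 4 samples each: 200 × 4 + 100 × 4 = 800 + 400 = 1,200, as in Table 4.
- Sampling occasions across both arms: 600 × 4 = 2,400.

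**What each option for the label field would reveal**
- *Arm printed:* 300 of the 600 are on placebo, so the field separates the two groups and discloses allocation.
- *Period printed:* Section 3.1 describes one 45-day double-blind phase, the same in both arms. Nothing is disclosed.
- *Analyte name printed:* placebo subjects are sampled too, so this does not unblind.

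Attachment 3 lets the first two stand as alternatives and says nothing about coding or masking the arm.

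**Ceiling on exposure if the arm were printed**
- Share of randomized subjects: 600 / 8,000 = 7.5%; 600 / 12,000 = 5.0%.
- Planned pooled rate (Section 11.2: 2.5% on placebo, 40% relative reduction, 1:1): rivaroxaban 2.5% × 0.6 = 1.5%; pooled (2.5% + 1.5%) / 2 = 2.0%.
- Events among 600 subjects at 2.0%: 600 × 0.020 = 12, and 12 / 161 = 7.5%.
- If 161 events needed all 12,000 subjects: 161 / 12,000 = 1.34%; 600 × 0.0134 = about 8, and 8 / 161 = 5.0%.

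Both counts run from randomization to Day 45 and assume that PK subjects have the trial-wide event rate. The first sampling visit is Day 7 with a window of −2/+5 days, that is Day 5 to Day 12. Events before a label is seen cannot be affected by it, so the true number is lower. The documents give no distribution of event times from which to say by how much.

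**The case against.** The strongest reply is that a compliant label need not disclose anything. The field is an either/or, and printing the period satisfies it. The wording reads like generic text meant to serve crossover and parallel designs alike. Printing each subject's true arm would also require allocation to leave the IWRS, and no section provides for that. Read together with Section 5, a label showing the arm would breach the protocol. All of this stands, and it limits the point to what the text permits.

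On consequences, the scripted questions are put to every subject, and suspected PE, DVT and bleeding must all go to adjudication. Nor do the documents say that the staff who process tubes are the staff who decide on testing. This weakens the route to bias, but discretion over the work-up remains.

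A reader might infer from Attachment 3 that site staff would see the allocation of 600 subjects, or that some 12 primary events were open to bias. The documents do not support either reading. They do not show what was printed. Attachment 3 refers to a Study Lab Manual for shipping, which is not among the documents, and it lets alternative procedures be approved without an amendment. The 12 is the upper end of a ceiling, and under the period option the exposure is zero.

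The reply does not remove the inconsistency. In a trial with a single treatment period, arm is the natural reading of the field, and nothing in either document tells whoever prepares the labels to omit, code or mask it.

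**Conclusion.** The point holds as an inconsistency in the protocol: Attachment 3 permits the treatment arm on labels that sites handle, while Section 5 keeps that information from investigators. It is not evidence that the blind was broken.

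If the arm were printed, up to about 600 subjects (5.0% of 12,000 to 7.5% of 8,000) could have their allocation read from a tube, and at most about 8 to 12 of the 161 targeted primary events would arise in them. These figures rest on the sub-study filling to 600, on 161 events being reached, on PK subjects having the average event rate, and on no allowance for events before the first sampling visit. If the trial stopped at 12,000 with fewer than 161 events, the count would fall in proportion and the 5.0% share would stay the same.

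The case for changing the text rests on the fix being nearly free and on the endpoint depending on site work-up. It does not rest on a demonstrated bias.

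**What to change.** In Attachment 3, delete the treatment arm from the label content. Alternatively, state that PK labels carry only blinded identifiers: study number, CRF I.D., scheduled sampling day and time, and analyte. The treatment period may stay or go, since it discloses nothing. Then check the label proof, and any stock already printed, to confirm that no allocation appears.

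The cost is one phrase and one check. The remaining items still identify each sample by subject and time point, the assay is unaffected, and no new step for releasing randomization codes needs to be written.
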